**SCREENING VISIT #1-A**

(for those participants who previously screen failed and are now eligible secondary to change in inclusion/exclusion criteria)

Re-consent (if necessary)

Repeat of all study requirements for screening visit #1.

**SCREENING VISIT #2 (within 2 weeks of screening visit #1)**

Adverse event assessment

Fasting Labs: Glucose, lipids and triglycerides) - (1) 3.5ml gold top tube

**STUDY VISIT #1 (Day 0) (within 1 month of screening visit #2)(+/- 1 week)**

Labs: venous blood sample for gene expression (3) 2.5ml Pax RNA tubes (total 7.5ml)

Cytokines (9ml for plasma (purple EDTA tube), 10 ml for serum (red top tube); **\*\*\*labs**

**drawn prior to flu vaccine)**

POCT - urine pregnancy test

Adverse event assessment

Administration of the influenza vaccine intramuscularly (IM): Vaccination with quadrivalent 2016-2017 vaccine A/California/7/2009 (H1N1); A/Hong Kong/4801/2014 (H3N2); B/Brisbane/60/2008(B/Victoria lineage); B/Phuket/3073/2013 (B/Yamagata lineage). Participants of normal weight will be injected IM with a needle of 1 to 1.5 in length. Obese individuals (defined as BMI>25) generally will require the use of a 2 in length needle to assure that the injection reaches the muscle. The needle length used for injection will be documented in the medical record.

Total blood volume to be drawn for visit #1 = 26.5ml

**STUDY VISIT #2 (Day 1 with no window)**

Labs: gene expression profile (blood volume = 7.5 ml)

Adverse event assessment

**STUDY VISIT #3 (Day 7 (+/-1 day)**

Labs: gene expression - (3) 2.5ml Pax RNA tubes (total 7.5ml)

Research Blood: Cytokines (9ml for plasma (purple EDTA tube), 10ml for serum (red top tube)

Total amount of blood drawn for visit #3 = 26.5ml

Adverse event assessment

**STUDY VISIT #4 (Day 28 +/- 2 days)**

Labs: gene expression - (3) 2.5ml Pax RNA tubes. (total 7.5ml)

Influenza A & B antibodies - (1) 10ml red top tube

Research Blood: Cytokines (9ml for plasma (purple EDTA tube), 10ml for serum (red top tube)

Total blood volume to be drawn for study visit #4 = 36.5ml)

Adverse event assessment

**STUDY VISIT #5 (Telephone visit) (Day 60 +/- 7 days)**

Adverse event assessment

**STUDY VISIT #6 (Day 90 +/- 7 days)**

Labs: gene expression (3) 2.5ml Pax RNA tubes. (total 7.5ml)

Influenza A & B antibodies - (1) 10ml red top tube

Research Blood: Cytokines (9ml for plasma (purple EDTA tube), 10ml for serum (red top tube)

Total blood volume for study visit #6 = 36.5ml

Adverse event assessment

**Unscheduled Study Visits:**

Study subjects may be asked to return to the RUH OPRC for additional bloodwork taken in the event of abnormal or missing labs.

**RESEARCH LABS**

**Analyze blood sample and serum for evaluation of the immune response to influenza:****1/ Hemagglutination inhibition assay**

Determine antibody titers against each strain of influenza included in the quadrivalent 2016-2017 vaccine: A/California/7/2009 (H1N1); A/Hong Kong/4801/2014 (H3N2); B/Brisbane/60/2008(B/Victoria lineage); B/Phuket/3073/2013 (B/Yamagata lineage) as described in similar studies (10, 11).

**Neutralization assay**

Determine the presence of specific neutralizing antibodies to influenza viruses in human sera following the protocol described by the WHO.

[http://www.who.int/influenza/gisrs\\_laboratory/2010\\_12\\_06\\_serological\\_diagnosis\\_of\\_influenza\\_by\\_microneutralization\\_assay.pdf](http://www.who.int/influenza/gisrs_laboratory/2010_12_06_serological_diagnosis_of_influenza_by_microneutralization_assay.pdf)

**3/ RNA-seq analysis of the peripheral blood**

RNA was obtained from peripheral blood using PAXgene RNA stabilization tubes placed at -80C post collection. RNA purification Quality of the RNA was assessed using the Agilent Bioanalyzer from the Genomic resource center. RNA-seq analysis will be performed by the Genomic resource center Illumina HiSeq 2500 Sequencing (50bp Single Read Sequencing).

Approximately 180 ml of blood (12 Tbsps.) will be obtained from each participant in the study.

Study participants whom are determined to have the metabolic syndrome will be referred to their primary care physician for treatment or will be referred to a healthcare clinic by the RUH social worker for treatment.

[name], DNP, ANP, will refer potential participants to [name] for possible entrance into this study.

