## 7.0 Study Description

### 7.1 \* Lay Summary

Please provide a summary of your study in lay language. The summary should be no more than a half page (500 words or less) and should contain a clear statement of the rationale for the study.

The development of industrialization with increased food consumption and sedentary has given rise to an obesity pandemic, which affects up to 30% of the population in countries like US, these populations being at greater risk for cardiovascular diseases, and diabetes. More than obesity per se, visceral obesity is associated with metabolic diseases (1) that cluster together and clinically defined metabolic syndrome (MetS). MetS comprises individuals with at least three of the 5 of the following factors: abdominal obesity, high blood triglycerides, low HDL ("good cholesterol"), high blood pressure and elevated fasting glucose (2). Metabolic syndrome is associated with a low-grade inflammation or metaflammation characterized by an infiltration of immune cells particularly in the adipose tissue, the liver and the pancreas (3) that is thought to be responsible for the induction of insulin resistance. It is thought that obesity predisposes to other diseases such as cancer, asthma but only little attention has been given to infectious diseases (4, 5). Studies have shown that obesity increases the risk of severe influenza infection (6) and associated death and reduces the efficacy of influenza vaccine in the obese population (7) but yet, the molecular mechanisms have not been described. Immune dysfunctions associated with obesity are suspected to play a major role but obesity is often associated with respiratory disorders that could directly explain the increased susceptibility to influenza infection (8). Also, metabolically healthy obesity is less associated with metaflammation (9). Therefore, we would like to focus particularly on metabolic syndrome, and determine how it influences immune response to viruses. We are thus hypothesizing that differences in the innate immune responses between individual with or without metabolic syndrome impact viral infection and vaccine outcome. Recent studies involving complex biological analysis and computational modeling have shown that the ability of an individual to positively respond to influenza vaccine can be molecularly predicted by looking at markers in the blood cells (10-12). We will perform seasonal influenza vaccination in people with or without metabolic syndrome to determine if the late adaptive response assessed by antibodies titers is different between the two groups and correlates with the early immune response assessed by gene expression profile in whole blood cells. Healthy nutritional habits along with increased physical activities should be best at preventing the development of metabolic syndrome but socio-economical issues are slowing the implementation of these changes. Therefore, as metabolic syndrome is raising public health concerns, it is important to understand why the metabolic syndrome affects susceptibility to diseases. The project we propose will contribute to a better understanding of the inflammatory phenotype associated with metabolic syndrome and establish for the first time if it affects the immune protection against infectious diseases and particularly against influenza virus infection. Our results are important to determine if the population affected by metabolic syndrome should receive anti-influenza treatment in priority in the context of a severe influenza epidemic.

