To support our hypothesis, several studies have demonstrated that during the 2009 influenza H1N1 pandemic, obesity was associated with more severe infection and death (6, 14). The mechanism is likely immune mediated but has not been determined yet (15). Also, it has been reported that obese people might be less protected by influenza vaccination (7). The area of systems biology has considerably contributed to a better understanding of vaccine efficacy (10, 16). Gene expression studies using peripheral blood can predict vaccine response to influenza (10, 11). High vaccine response correlates with the expression of interferon signaling (genes like STAT1, IRF9) and antigen processing and presentation. To test our hypothesis, we contacted the authors of a study published in Cell in 2014 (12) and obtained the BMI of the patients. The study demonstrated the ability to predict the influenza vaccine response using several parameters. We focused on the immune response based on antibody titers and the gene expression profile at D0 and D1. We separated the individuals in 2 groups: one group of lean (BMI<25) and one group overweight and obese (BMI>25). The two groups contained 25 and 17 individuals respectively. We observed a trend towards an inverse correlation of the immune response to influenza vaccine with increasing BMI. Also, we analyzed the differential gene expression profile between D0 and D1 between the two groups. JUN Kinase, Stat1 and IRF1 were among the most up-regulated genes in the lean group but not in the overweight and obese group. When comparing the two groups using ingenuity pathway analysis, the role of PKR in interferon response, Toll like receptor signaling, Natural killer cell signaling were more activated in the lean group compare to the overweight and obese group. These results indicated that the innate immune response induced by the vaccine might be attenuated in the overweight and obese group. BMI was the only factor used for this analysis and we did not have access to any metabolic marker. Obesity is not necessarily associated with an unhealthy metabolic status. Therefore, we would now like to focus on metabolic syndrome as it better correlate with an unhealthy metabolic status. Our aim is to determine if metabolic syndrome attenuates the immune protection induced by the vaccine and establish the molecular mechanism of antiviral immune deficiency associated with metabolic syndrome. We would like to know if differences between people with and without metabolic syndrome can be seen at the molecular level and correlate with differences in antibody titers. We believe our study will contribute to 1/ better understand vaccine efficacy 2/ establish if the low-grade chronic inflammation associated with metabolic syndrome impacts the systemic immunity against viral infection.

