**SCREENING VISIT #1**

Consent

Medical history

Physical examination including height and weight to determine BMI, and waist circumference

Vital Signs - If the initial blood pressure is above 150/90 mmHg upon arrival to the OPRC, a second B/P will be taken by the LIP during the screening process. The average of the two readings will be the enrollment criterion.

POCT - HIV

POCT - urine pregnancy test

Labs: HbA1c - (1) 3.0 ml lavender tube

Hepatitis Panel - (1) 8.5ml SST marble top tube

Comprehensive metabolic & CRP - (1) 8.5 ml SST marble top tube

CBC - 3 ml lavender top tube

Gene expression - (3) 2.5ml Pax RNA tube (total 7.5ml).

Influenza A & B antibodies - (1) 10ml red top tube

Total blood volume to be drawn for screening visit 1 = 40.5ml .

Instructions to return fasting for 8 hours prior to the next visit.

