**Statistical Analysis**

To compare the means of antibody titers between groups (healthy volunteers and metabolic syndrome participants) a t-test at 95% significance level will be performed if the data follows a normal distribution, otherwise a non parametric Wilcoxon-Mann-Whitney test will be used.

A Chi-square test at 95% significance level will be used for the comparison of percentage of participants achieving a determined level for the HI antibody titer and rates of seroconversion. On that case if any observed frequency is smaller than 5 Fisher exact test will be used instead of Chi-square.

Expression values will be modeled using mixed-effect models, with group as fixed factor, and a random effect for each participant. FCHs for the comparisons will be estimated, and hypothesis testing conducted.

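### Whole-blood gene expression is modelled with no account of white-cell mix, so a composition difference could be read as altered signalling, mainly for genes restricted to one cell type

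*Combined protocol and SAP*

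**What the plan says.** Gene expression is a secondary outcome (section 11.6); the aim and primary outcome concern antibody response (11.4, 11.5). Section 11.7 describes the specimen as whole blood: "RNA was obtained from peripheral blood using PAXgene RNA stabilization tubes placed at -80C post collection". PAXgene tubes are drawn at Screening Visit 1 and on Days 0, 1, 7, 28 and 90.

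The stated model, under Statistical Analysis, is: "Expression values will be modeled using mixed-effect models, with group as fixed factor, and a random effect for each participant". Fold changes and tests for unspecified comparisons follow. The text names no day term, cell count, cell fraction, deconvolution or related sensitivity analysis.

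One blood count is listed, at Screening Visit 1: "CBC - 3 ml lavender top tube". No differential and no analytic use are stated.

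The lay summary (7.1) uses expression as a correlate of the antibody result, asking whether that result "correlates with the early immune response assessed by gene expression profile in whole blood cells". Section 11.1 goes further. It reports a preliminary Day 0 to Day 1 comparison by BMI group in which, among other pathways, "Natural killer cell signaling were more activated in the lean group compare to the overweight and obese group", and concludes: "These results indicated that the innate immune response induced by the vaccine might be attenuated in the overweight and obese group". It also gives finding the molecular mechanism of the antiviral deficit as part of the aim.

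**The concern.** A transcript level in unfractionated blood reflects two things: how strongly each cell expresses the gene, and how many cells of each type are in the tube. If the cohorts differ in the share of a cell type, transcripts restricted to that type differ too, with nothing changed inside any cell. If the share moves after vaccination in one cohort only, the Day 0 to Day 1 response differs between cohorts for the same reason.

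Fewer circulating natural killer cells and weaker signalling per natural killer cell are different mechanisms, yet the planned output would look alike. The participant random effect does not separate them. It absorbs stable differences between individuals, but not a mean difference between cohorts or a shift in cell mix after vaccination. A larger sample would not help either, because this is bias rather than noise.

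**Working it through.** The plan states no figure for the expression outcome, so there is none to reproduce. The check has a document part and an illustration.

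**1. Is cell composition measured when RNA is drawn?** Itemised tubes in section 11.7 against the stated totals:
- Screening 1: 3 + 8.5 + 8.5 + 3 (CBC) + 7.5 + 10 = 40.5 ml, as stated.
- Days 0 and 7: 7.5 + 9 + 10 = 26.5 ml, as stated.
- Day 1: 7.5 ml, expression only.
- Days 28 and 90: 7.5 + 10 + 9 + 10 = 36.5 ml, as stated.

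The totals after screening are met without a CBC tube. The flow-cytometry items in section 36.1 are unticked. The procedure table in 13.1 is cut off in the text available, so a count listed only there cannot be excluded, but the volumes argue against it.

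**2. How old is the one count by Day 0?** Screening 2 may follow 2 weeks later, and Day 0 a further month later with a 1-week window: 14 + about 30 + 7 = up to about 51 days. It shares a visit with one PAXgene sample but cannot track Days 1 or 7.

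**3. Apparent fold change from composition alone.** Let f be the share of a cell type and R its expression relative to all other cells, with per-cell expression identical in both cohorts:

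fold change = [f1·R + (1 − f1)] / [f0·R + (1 − f0)], which becomes f1/f0 when the gene is exclusive to that type.

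The documents give no shares, so these are assumed:

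| Shares | Exclusive | R = 20 | R = 5 | R = 2 |
|---|---|---|---|---|
| 6% v 8% | 1.33 | 1.18 | 1.07 | 1.02 |
| 6% v 9% | 1.50 | 1.27 | 1.10 | 1.03 |
| 30% v 20% | 0.67 | 0.72 | 0.82 | 0.92 |

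For example, 6% v 9% at R = 5: (0.45 + 0.91)/(0.30 + 0.94) = 1.36/1.24 = 1.10.

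**4. Would a group test detect it?** With 20 per group and an assumed between-person log2 SD of 0.5, the standard error of the cohort difference is 0.5 × √(2/20) = 0.158. For 6% v 8% the log2 shifts are 0.415, 0.236, 0.090 and 0.027 across the four columns, or 2.6, 1.5, 0.6 and 0.2 standard errors. For the exclusive gene, the chance of nominal p < 0.05 is about 99%, 75% and 47% at SDs of 0.3, 0.5 and 0.7 (normal approximation).

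A simulation agrees (2,000 runs; exclusive gene; log2 SD 0.3 for the share and 0.4 residual, so total √(0.09 + 0.16) = 0.5). With no per-cell difference, the group-only model rejects in 5%, 29%, 71% and 95% of runs for 6% against 6%, 7%, 8% and 9%. With the true share as a covariate it rejects in 5–6%.

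**5. Does this carry over to the Day 0 to Day 1 change?** For an exclusive gene, log2 expression is log2(f) plus log2(per-cell level). If f is 6% in one cohort and 9% in the other on both days, log2(f) drops out of each person's change. The cancellation is exact here, and also when all cell types respond alike; otherwise it is approximate. A clear bias in the group-by-day contrast therefore needs f to move between days differently in the two cohorts.

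**The case against.** Much of the opposing case stands.

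- **No composition difference is documented.** Section 11.1 describes immune cells infiltrating tissue and primed pathways. It does not say that circulating white-cell proportions differ. A reader might infer that the cohorts do differ and that the result will be misread; the text supports only that it could be.
- **Most of the preliminary findings are not tied to a cell type.** The genes and pathways listed in 11.1 include JUN kinase, STAT1, IRF1, PKR in the interferon response and Toll-like receptor signalling. Only natural killer signalling names a cell type. A reader might infer that an interferon signal could not be told from a monocyte count, but nothing in the documents makes those genes specific to one cell, and the table shows how quickly the effect fades.
- **The main rationale contrast is a within-person change**, from which a stable difference largely cancels.
- **Whole blood is a reasonable choice.** For predicting antibody response, composition is legitimate signal.
- **Adjustment is imperfect.** The 5–6% rejection rate used the true share. It does not show that fractions deconvolved from the same RNA would do as well. Adjustment may also remove real recruitment effects.

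The objection does not remove the gap. The plan aims at mechanism, reads a natural killer contrast as an attenuated response, and names nothing that would separate the two explanations. Excluding infection in the week of a visit (12.12) limits one cause of count shifts but measures nothing.

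**Conclusion.** The point holds in a limited form. Because unfractionated blood is modelled with cohort and participant alone, a cohort difference in cell mix could appear as a cohort difference in expression. A cohort-specific shift after vaccination could appear as a different early response.

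The size depends on assumed shares and on how restricted the gene is: 1.50-fold for an exclusive transcript at 6% v 9%, and 1.03-fold at twofold enrichment. Natural killer transcripts are the most exposed and broadly expressed genes little affected. The rejection rates above also rest on assumed SDs and a nominal per-gene 0.05 level.

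A reader might go further and conclude that the expression outcome is invalid. The documents do not support that. Its use as a correlate of antibody response is untouched, as is the primary outcome. Only the mechanistic interpretation in section 11.1 is exposed.

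**What to change.** Add a prespecified sensitivity analysis to Statistical Analysis:

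1. State the day term, and define the group and group-by-day contrasts.
2. Estimate the major cell-type fractions from the RNA-seq data already planned. Check them against the Screening 1 CBC and the PAXgene sample from that visit, where a differential is available.
3. Report each contrast unadjusted and adjusted for a small number of named fractions.
4. Where the two disagree, describe the result as a whole-blood expression difference that may reflect cell composition, not as altered signalling per cell.

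This needs no new visit, sample or participant. The costs are extra analysis work, some loss of precision with 20 per group, estimated fractions that may be biased if marker genes are themselves regulated, and possible removal of real recruitment effects. The last two are why both versions should be reported.

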**11.8 \* Data Analysis**

Describe method(s) of data analysis. Include the role of external collaborators as appropriate.

As per recommended by the food and drug administration (17), the hemagglutination inhibition (HI) antibody assay has been used to assess vaccine activity and may be appropriate for the evaluation of the pandemic influenza vaccine. Appropriate endpoints may include: 1) the percentage of subjects achieving an HI antibody titer  $\geq 1:40$ , and 2) rates of seroconversion, defined as the percentage of subjects with either a pre-vaccination HI titer  $< 1:10$  and a post vaccination HI titer  $> 1:40$  or a pre-vaccination HI titer  $\geq 1:10$  and a minimum four-fold rise in post-vaccination HI antibody titer. Previous study have built models using both HAI and neutralization assays to determine vaccine responsiveness.

The RNA-seq analysis will be run with the help of the Genome resource center as well as the expertise of [name] listed as a collaborator of this project.

**11.9 \* Explain the rationale for the choice of statistical measures and the number of subjects proposed for the study, including the power calculations when applicable.**

Since no preliminary data is available to estimate the percentage of participants achieving a determined level for the HI antibody titer and the rate of seroconversion for each group (healthy volunteers and metabolic syndrome participants) we provide an estimation of the minimum effect size for the sample size selected is able to detect. For a sample size of 40 participants, 20 at each group, a 95% significant Chi-square test will be able to detect an effect size equal or larger than 0.56 with 0.8 power. It means that a Chi-square test will be able to detect independence between groups if the distance between the observed odd ratio is larger than 1.56.

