**11.4 \* Aim(s)**

Indicate how you will *address the hypothesis* (e.g., to compare groups, to estimate a parameter, to ascertain feasibility). Since the sample size determination is usually based on the primary aim only, the primary aim should be sufficient to justify the study.

Antibody response post influenza vaccine will be compared between subjects with the metabolic syndrome and healthy lean controls

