**11.5 \* Primary Outcome(s)**

Indicate which *variable(s)* will be assessed to judge the primary specific aim. Give measurement units, if applicable.

Antibody titers and vaccine response (hemagglutinin)

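### The HI ≥1:40 comparison ignores the pre-vaccination titre, so prior immunity dilutes it and, if unequal between cohorts, biases it; seroconversion already uses baseline

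*Combined protocol and SAP*

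**What the plan says.** Section 11.4 states the aim: "Antibody response post influenza vaccine will be compared between subjects with the metabolic syndrome and healthy lean controls". Section 11.5 makes antibody titres and vaccine response the primary outcome.

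Section 11.8 introduces the HI endpoints as ones that "may be appropriate for the evaluation of the pandemic influenza vaccine"; this trial gives a seasonal quadrivalent vaccine. It names two and does not rank them:

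- "the percentage of subjects achieving an HI antibody titer" of at least 1:40. The definition contains no pre-vaccination titre.
- Seroconversion. This uses the pre-vaccination titre: either below 1:10 before and above 1:40 after, or at least 1:10 before "and a minimum four-fold rise in post-vaccination HI antibody titer".

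The Statistical Analysis text under Section 11.9 assigns a chi-square test to the "comparison of percentage of participants achieving a determined level for the HI antibody titer and rates of seroconversion", with Fisher's exact test if any observed count is below 5. It names no covariate, stratum or subset based on baseline titre.

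A pre-vaccination sample is listed at Screening Visit #1: "Influenza A & B antibodies - (1) 10ml red top tube". The same tube recurs at Day 28 and Day 90. Section 12.12 excludes influenza vaccination only after June 1, 2016, and no criterion sets a titre limit. Section 16.1 matches controls on age (±5 years) and gender.

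**The concern.** The aim is response to the vaccine, but a post-vaccination titre of at least 1:40 describes status. A participant who starts at 1:80 and does not respond at all still counts as a success. Adults aged 18 to 65 with earlier infection or vaccination can enter, and nothing in the selection or matching equalises prior immunity between the cohorts.

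Two consequences follow for this endpoint. If prior immunity is equal in the cohorts, a true difference in response shrinks. If it is unequal, the comparison is biased: a difference can appear where the vaccine works equally well, or a real one can vanish. The baseline titre that would separate the two is needed for seroconversion anyway, but is not used here.

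**Working it through.** **The plan's own figure.** There is none to reproduce for this point. Section 11.9 says no preliminary data exist for either endpoint, so every baseline and response rate below is an assumption. The detectable effect size of 0.56 in Section 11.9 does not enter these calculations.

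**Inputs.** From the documents: 20 per group, 5% level (taken as two-sided), chi-square without continuity correction unless an observed count is below 5, then Fisher. Assumed: *b*, the share already at or above 1:40 (taken to stay there), and *r*, the share of the rest who reach 1:40.

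**Formula.** Share at or above 1:40 after vaccination: p = b + (1 − b)·r. Rejection probabilities are exact binomial enumerations under the plan's rule. "Restricted" below, used without quotation in the tables, means the same rule applied only to participants below 1:40 at baseline, averaged over the random number of them.

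**1. Equal response, r = 0.60 in both cohorts.** For b = 0.60, p = 0.60 + 0.40 × 0.60 = 0.84. For b = 0.20, p = 0.20 + 0.80 × 0.60 = 0.68.

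| Protected at baseline | p, cohort 1 vs 2 | Plan's test rejects |
|---|---|---|
| 60% vs 20% | 84% vs 68% | 13.7% |
| 50% vs 30% | 80% vs 72% | 4.8% |
| 50% vs 40% | 80% vs 76% | 2.9% |
| 40% vs 40% | 76% vs 76% | 2.4% |

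Restricted, the rejection rate is about 3% in each case. With r = 0.50 instead, the plan's test rejects 20.0% at 60% vs 20% and 6.4% at 50% vs 30%; restricted, 2.8% and 3.0%.

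**2. True difference, equal baseline, r = 0.90 vs 0.45.** The visible difference is (1 − b) × 45 points.

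| Protected in both cohorts | Visible difference | Power, plan's test | Power, restricted, same rule |
|---|---|---|---|
| 0% | 45 points | 85% | 85% |
| 20% | 36 points | 68% | 75% |
| 40% | 27 points | 48% | 58% |
| 50% | 22.5 points | 37% | 47% |

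**3. True difference, unequal baseline, r = 0.80 (controls) vs 0.40 (metabolic syndrome).**

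- b = 0.25 vs 0.75: 0.25 + 0.75 × 0.80 = 0.85 and 0.75 + 0.25 × 0.40 = 0.85. A true 40-point difference becomes zero. The plan's test rejects 2.0%; restricted, 28.8%.
- b = 0.20 vs 0.60: 84% vs 76%. The plan's test rejects 5.0%; restricted, 40.6%.

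**4. Separating baseline from the choice of test.** For the setting in step 2, an uncorrected Mantel-Haenszel score test can replace the plan's rule.

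| Protected | Plan's rule, all | Score test, all | Score test, below 1:40 |
|---|---|---|---|
| 20% | 68% | 79% | 81% |
| 40% | 48% | 62% | 68% |
| 50% | 37% | 52% | 59% |

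Changing the test alone adds about 11, 14 and 15 points (68 to 79, 48 to 62, 37 to 52). Using baseline then adds about 3, 6 and 7 (before rounding). With the plan's rule kept, using baseline adds about 7, 10 and 10 (step 2).

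**The case against.** Four objections carry weight.

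- **Seroconversion already conditions on baseline.** This stands. A participant starting at 1:40 or more seroconverts only with a four-fold rise. A reader might infer that the binary analysis ignores prior immunity altogether; the documents do not support that. But they do not rank the two endpoints, both are tested, and a result driven by baseline on the ≥1:40 endpoint could be reported as a primary finding.
- **A false difference needs a large imbalance.** This also stands. At 50% vs 30% the plan's test stays at 4.8% with a 60% response, or 6.4% with a 50% response. Nothing in the documents shows that the cohorts differ in prior immunity, so it would be wrong to infer that the plan will produce a false positive. Dilution, however, needs no imbalance, and masking works even when the test is conservative.
- **Much of the attainable power gain is not about baseline.** Comparing 68%, 48% and 37% with 81%, 68% and 59% invites the reading that stratification brings the whole gain. Step 4 shows that most of it comes from leaving the Fisher switch.
- **Status at or above 1:40 is a legitimate measure.** Agreed, as a description of post-vaccination status, and the plan does not call these participants responders. The mismatch arises when it is compared between non-randomised cohorts to judge vaccine response, as Sections 11.4 and 11.5 intend.

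**Conclusion.** The concern holds for the ≥1:40 comparison only. As written, it is an unadjusted test of post-vaccination status between cohorts whose prior immunity nothing equalises.

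The attributable loss is moderate when baselines are equal: about 7 to 10 points of power under the plan's own rule, for a true 90% vs 45% response with 20% to 50% already protected. With unequal baselines, the error ranges from negligible to serious: false rejection of 2.9% to 13.7% at a 60% response, and complete masking of a true 40-point difference at 25% vs 75%.

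These sizes rest on assumed rates and on protected participants staying at or above 1:40. The direction of the dilution does not depend on the particular rates chosen; the presence and direction of any bias cannot be known from the documents. The point merits a change of analysis wording, not of design.

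**What to change.** In Statistical Analysis, compare HI ≥1:40 stratified by baseline below 1:40 versus at or above it, with a Mantel-Haenszel or exact stratified test named in advance. Report the percentage reaching 1:40 among those below it at baseline, by cohort, and present it beside seroconversion. The crude percentage can remain as a description of status. State that the screening antibody sample supplies the baseline HI titre.

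The cost is wording only: no extra visit, blood draw or participant. The drawback is that the stratified test rests mainly on those below 1:40, about 20 × 0.5 = 10 per group if half are already protected, and 6 per group if 70% are. Logistic regression on log2 baseline titre is an alternative, but with 40 participants and nearly all high-baseline participants positive, ordinary maximum likelihood may fail through separation. If regression is chosen, specify a penalised or exact version.

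### The seroconversion rule fails a seronegative participant who reaches exactly 1:40 but passes one who makes the smaller rise from 1:10 to 1:40

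*Combined protocol and SAP*

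**What the plan says.** Section 11.8 names two binary endpoints based on the HI titre.

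- The first is "the percentage of subjects achieving an HI antibody titer $\geq 1:40", an inclusive cut-off.
- The second is seroconversion, which has two branches. With a pre-vaccination titre below 1:10, the participant must also meet the condition "and a post vaccination HI titer $> 1:40". With a pre-vaccination titre of 1:10 or more, the requirement is "a minimum four-fold rise in post-vaccination HI antibody titer".

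The Statistical Analysis text under 11.9 then commits to a Chi-square test, or Fisher's exact test when a cell is small, for the "comparison of percentage of participants achieving a determined level for the HI antibody titer and rates of seroconversion". The sample-size paragraph in 11.9 is framed around the same two percentages. No other section gives a different seroconversion cut-off or says how a post-vaccination titre of exactly 1:40 is classified.

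**The concern.** A seroconversion rule should not rank a larger rise below a smaller one that ends at the same titre. As written, this one does: two participants both finish at 1:40, and the one who started lower is the non-responder.

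The error falls only on participants who are seronegative at baseline. It therefore lowers the seroconversion rate in proportion to how many seronegatives a group contains. If the metabolic syndrome and control groups differ in baseline serostatus, the strict sign adds a difference between them that is not a difference in response. Section 16.1 matches controls on age and gender only. Section 12.12 excludes vaccination after June 1, 2016, but nothing controls vaccination in earlier seasons. Section 11.7 measures four strains, so the misclassification can recur for each.

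**Working it through.** **1. Apply the rule as written.** The inequalities come from 11.8. The two-fold series, and the coding of <1:10 as 1:5 used for the bracketed fold-rises, are assumptions because the documents give neither.

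| Pre | Post | Fold-rise | Rule as written | With ≥1:40 |
|---|---|---|---|---|
| <1:10 | 1:20 | more than 2 (4 if coded 1:5) | no | no |
| <1:10 | 1:40 | more than 4 (8) | **no** | **yes** |
| <1:10 | 1:80 | more than 8 (16) | yes | yes |
| 1:10 | 1:40 | 4 | yes | yes |
| 1:20 | 1:40 | 2 | no | no |
| 1:20 | 1:80 | 4 | yes | yes |
| 1:40 | 1:160 | 4 | yes | yes |

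The second and fourth rows show the reversal. It does not depend on the coding: from any value below 10, a rise to 40 exceeds 40/10 = 4-fold. Replacing > by ≥ changes the second row and no other pair.

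**2. How often a seronegative participant lands on exactly 1:40.** The plan states no figure to reproduce, so this step is illustrative. Assume log-normal post-vaccination titres, read to the nearest two-fold dilution. With d = log2(40/GMT) and SD s on the log2 scale,

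P(exactly 1:40) = Φ((d + 0.5)/s) − Φ((d − 0.5)/s).

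| GMT | d | s = 1.5 | s = 2 |
|---|---|---|---|
| 40 | 0 | 0.26 | 0.20 |
| 80 | −1 | 0.21 | 0.17 |
| 160 | −2 | 0.11 | 0.12 |

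For GMT 80 and s = 1.5:

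- P(≥1:40) = 1 − Φ(−1.5/1.5) = 1 − 0.159 = 0.84.
- P(>1:40) = 1 − Φ(−0.5/1.5) = 1 − 0.369 = 0.63.

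Seroconversion among seronegatives reads 63% instead of 84%.

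**3. Effect on one group.** The plan has 20 per group (11.9). If a share f is seronegative and a share q of those land on 1:40, then 20 × f × q participants are reclassified. For f from 20% to 80% and q from 10% to 30% (assumed ranges), this runs from 20 × 0.2 × 0.1 = 0.4 to 20 × 0.8 × 0.3 = 4.8 participants, or 2 to 24 percentage points per strain.

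**4. Effect on the comparison.** Suppose 60% of one group and 30% of the other are seronegative, with the same titre distribution among seronegatives in both. The strict sign adds a difference of (0.60 − 0.30) × P(exactly 1:40), which runs from 0.30 × 0.11 = 0.033 to 0.30 × 0.26 = 0.078. That is 3 to 8 percentage points, or about 0.7 to 1.6 participants of 20.

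**5. Whether one participant can matter.** With 14/20 against 7/20, the uncorrected Chi-square is 40 × (14×13 − 6×7)² / (20×20×21×19) = 4.91, p = 0.027. Moving one participant to give 13/20 against 7/20, it is 40 × (13×13 − 7×7)² / (20×20×20×20) = 3.60, p = 0.058. No cell falls below 5, so the plan's switch to Fisher's test does not apply.

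**The case against.** The strongest case on the other side concerns weight, not existence. The comparison of mean titres does not use this rule, and neither does the ≥1:40 endpoint, so one of three HI readouts is affected, and only for one pre/post pair. The rule can be corrected from stored titres without new data. Section 11.8 introduces its endpoints tentatively and takes them from cited guidance, so a slip in paraphrase is likely. All of this is fair. But the Statistical Analysis text commits to testing seroconversion, and the only definition it can draw on is this one. A text-reading fault is unlikely, because the greater-or-equal sign appears correctly twice in the same sentence.

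The illustrative sizes are assumed, and this objection stands. The documents give no dilution series, titre distribution or baseline serostatus. Rounding down to the dilution at or below the value, instead of to the nearest, gives about 75% against 50% at GMT 80 and SD 1.5, in place of 84% against 63%. The share on exactly 1:40 is then 15% to 25% over the same grid. Nothing in the documents shows that baseline serostatus differs between groups.

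Two further points also stand. Disagreement with the first endpoint is weak evidence by itself, since someone at 1:40 both before and after vaccination passes that endpoint and fails seroconversion under any version. And if <1:10 is coded 1:5, the corrected rule still asks an eight-fold rise of seronegatives against four-fold of the rest. The correction reduces sensitivity to baseline mix but does not remove it.

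**Conclusion.** The rule is wrong as written. The reversal between <1:10 to 1:40 and 1:10 to 1:40 follows from the stated inequalities and needs no assumption about titres. The documents give no reason for a stricter bar in seronegatives.

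The effect on results cannot be computed from the documents. Under the stated assumptions (two-fold series, nearest-dilution rounding, log-normal titres), 11% to 26% of seronegatives would be miscounted. The 3 to 8 point distortion between groups also requires a 60% against 30% split in baseline seronegativity. It is the part added by the strict sign, over and above any difference the corrected rule would show. At 20 per group each participant is 5 percentage points, so even a small miscount can move a borderline test across 0.05.

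**What to change.** In 11.8, define the seronegative branch as a pre-vaccination HI titre <1:10 with a post-vaccination HI titre ≥1:40. The two branches then no longer reverse the order of response, and the cut-off matches that of the first endpoint. Make the change before titres are analysed, so that it cannot be influenced by the results. If a strict cut-off was intended, the plan should say so and give the reason.

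The cost is one symbol. No visit, sample, assay or sample size changes.
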